#### CQI

We will collect data via 1:1 interviews using semi-structured interview guides. All interviews will be conducted over Zoom or Facebook Messenger with participants located in a private area of their choosing. The participants who cannot secure a private area for the interview will have an option to attend the online interview from one of the study offices following COVID-19 safety protocols. We will not record participants' names or other personal identifiers (except for voice recording). All interviews will be audio-recorded and transcribed verbatim. To ensure confidentiality of REHN data, the interviews with REHN staff will be conducted by Graduate Research Assistants, Emory; the study leadership and management team ([name], [name], [name] and [name]) will not have access to REHN interview transcripts. Interviews with the pharmacists and intervention participants will also be conducted by Graduate Research Assistants, Emory. The interviews will take about 60 to 90 minutes. There will be no follow-up with the participants. The audio-recordings will be stored at encrypted and password-protected computer network until the end of CAER2HOPE study and then will be deleted.

Participant interview guide: we are expanding the interview domains covered to include the perceived effectiveness of the intervention. These qualitative data will complement quantitative data on intervention effectiveness, by illuminating perceived pathways through which the intervention might (or might not) have worked, and also allow us to explore participant perceptions of effectiveness. The

revised guide is attached (data collection section).

### Attachments

Attach Type	File Name
ResearchProcedures	Participant Notification Text 033022.pdf
ResearchProcedures	Recruitment Email Text and Phone Scripts 020422.pdf
ResearchProcedures	Screener 081721 - Clean.pdf
ResearchProcedures	Fentanyl Quiz 061521.pdf
ResearchProcedures	Naloxone Brochure 120420.pdf
ResearchProcedures	Intervention Individual Risk and Needs Assessment 111820.pdf
ResearchProcedures	Rapport Script.pdf
ResearchProcedures	C2H Retention Flyer 061020 - Clean.pdf
ResearchProcedures	C2H Retention Flyer 061020 - PR Approval.pdf
ResearchProcedures	Pre-Appointment (Normal Operations).pdf
ResearchProcedures	Pre-Appointment (phone).pdf
ResearchProcedures	Missed Appointment (Normal Operations).pdf
ResearchProcedures	Missed Appointment (phone).pdf
ResearchProcedures	Letter to Contact (Normal Operations).pdf
ResearchProcedures	Letter to Contact (phone).pdf
ResearchProcedures	Recruitment Presentation Text 031820 - Clean.pdf
ResearchProcedures	Recruitment Letter - Personalized for G2H.pdf
ResearchProcedures	Jail Handout Good Samaritan and Naloxone Laws - Clean.pdf
ResearchProcedures	recruitment letter.pdf
ResearchProcedures	Jail Handout - PR Approval 101719.pdf
ResearchProcedures	Jail Handout - PR Clean 101719.pdf
ResearchProcedures	NIDA Modified ASSIST.pdf
ResearchProcedures	Pre-release Appointment Card.pdf
ResearchProcedures	Post-release Appointment Card.pdf

### Data Collection & Research Materials

In this section, please provide the following:

- Describe all sources or methods for obtaining research materials about or from living individuals (such as specimens, records, surveys, interviews, participant observation, etc.), and explain why this information is needed to conduct the study.
- For each source or method described, please list or attach all data to be collected (such as genetic information, interview scripts, survey tools, data collection forms for existing data, etc.).
- If you will conduct a record or chart review, list the beginning and end dates of the records you will view.

Process data tracked by staff: Fidelity will be assessed through the Project Manager who will review case notes for 10% of randomly selected sessions. Reach will be assessed calculating the percent of eligible individuals who enroll (e.g., the # enrolled divided by the number of individuals who screen eligible for START-C2H). Dose will be assessed by calculating the percent of START-C2H sessions attended. START-C2H's immediate impact will be assessed via the START-C2H participants' survey data (described below) to assess immediate impacts on linkage to services.

Survey administration: START-C2H comparison condition and intervention participants will complete longitudinal data collection at pre-release session 1 (baseline part 1), at pre-release session 2 (baseline part 2) within 7 days of session 1, three months post-release, and 6 months post-release. Longitudinal data collection will be completed in the community for those recruited in the community. Baseline survey data will be collected in the jail or community (session 1) after enrollment and consent, in jail or community (session 2) within 7 days of session 1. Sections of the baseline survey will be repeated at START-C2H's in-person session, post-release or post-enrollment for those recruited in the community, including at 3-month session and in-person 6-month session, to assess change over time. Participants will complete surveys using computer assisted personal interviewing (CAPI); CAPI has been used previously in jails (and outside of jail) to assess START and is effective with low-literacy populations. In CAPI, the survey is displayed to study staff on a computer screen and the computer program lists the questions and responses and the study staff reads them aloud to the participant in person or by phone. We will use timeline follow-back methodology to improve participant recall (see attachment, Timeline Follow Back, for example of how this method is applied). To avoid social desirability and other forms of reporting bias, portions of the survey will be administered by an off-site staff person (i.e., rather than by the participant's re-entry health navigator) via UK's HIPAA-compliant instance of the web-conferencing platform called Zoom. Zoom is a cloud-based platform for video and audio conferencing, collaboration, chat, and webinars across mobile devices, desktops, telephones, and room systems (similar to Skype). UK supports two instances of Zoom -- one that is HIPAA compliant and one that is not HIPAA. UK has a signed Business Associate Agreement, providing a separate instance of Zoom that is HIPAA compliant. Data collection is possible as Zoom users can share their screens. Study staff will open a copy of the survey via Zoom, allowing a participant to view and answer questions orally while the staff member records the answer. Administration of the survey will take place in a private room to ensure privacy and confidentiality of data.

Survey content: Prospective participants will complete a screening survey (described above, see Screening Survey attached) to determine eligibility. Surveys (see START-C2H Survey appendix) will capture the following domains: (1) sociodemographic characteristics; (2) all possible behavioral targets; and (3) health and social service engagement. The survey will closely resemble that

used in the currently approved CARE2HOPE study under IRB protocol #43520. Of note, the survey instructions will clearly indicate that time periods at baseline refer to time before incarceration and, when repeated for follow-up visits, recall periods will be adjusted accordingly (i.e., language referring to lifetime or past 6 month behavior will be changed to past 3 months). Surveys will take 45-60 minutes to complete (survey administration methods are described above).

Drug screening: We will conduct Urine or saliva drug Screens at the 1-week, 3-month, and 6-month appointments. We will not conduct drug screening in the jail. As in CARE2HOPE UG3 phase (Protocol #43520), we will use HomeHealth's iCup Drug Test that tests for 13 drugs including opiates (heroin and morphine), buprenorphine, methadone, oxycodone, as well as various stimulants, sedatives, and other drugs. For saliva test, we will use SalivaConfirm (TestCountry, San Diego, CA) drug screening kit that detects 10 types of illicit drugs in the sample in 10 minutes.

HIV Testing: The REHN will conduct HIV testing using the rapid-rapid protocol approved for HIV surveillance and confirmatory testing by the state health department and CDC. Participants will be tested using rapid INSTI HIV 1/HIV 2 Rapid AntibodyTest (bioLytical Laboratories, USA), which is a 60-second immunoassay for the detection of HIV-1 and HIV-2 antibodies in blood obtained from finger stick (sensitivity: 99.6, specificity: 99.3) followed by confirmatory re-testing with the Sure Check® HIV-1/2 Antibody Test (ChemBio Diagnostic Laboratories, Medford NY) on blood obtained from finger stick (sensitivity: 99.8, specificity: 99.9). When a participant tests HIV positive on BOTH of the rapid tests, they are considered to be confirmed as HIV positive and therefore require reporting to the state health department. Participants are informed of this reporting requirement and procedures involved in a case investigation in their informed consent form. Upon a positive test, we will complete the KY DPH's HIV Case Report form found here: <http://chfs.ky.gov/NR/rdonlyres/36B936F0-AD69-4B95-83A7-FE4E37201364/0/AdultCaseReportForm2016.pdf>. We will fill in the participant's name and contact information, information about our facility, participant demographic data, residential data, risk behavior data, treatment history, and testing history. We will not complete the section describing children of the participant. The REHN will complete a facilitated referral to their district Ryan [name] Part B HIV care coordinator for participants who test positive on both tests. More detail about safety precautions and referrals are described in sections below.

HCV testing. REHNS will use the OraQuick® HCV Rapid Antibody Test (OraSure, Bethlehem, PA), a 20-minute indirect immunoassay test to detect HCV antibodies in blood from fingerstick. Participants who test positive for HCV will be referred to UK Kentucky Clinic Digestive Diseases and Nutrition [contact]) or St. Claire Regional Medical Center in Morehead, KY or encouraged to visit their primary care doctor for confirmatory (HCV RNA) testing.

Locator form. The locator form shown in the Locator Form Appendix (attached) is identical to the existing CARE2HOPE locator form approved under IRB protocol (#43520). The form is a strong retention tool tailored to this population. This form queries contact information for the participant and multiple key network members, and seeks consent to contact network members as needed. Participants can opt into using Facebook messenger for retention contacts. Our locator form asks participants to indicate whether they give permission for us to contact them via private messenger on social media (i.e., Facebook messenger) and IRB-approved language informing participants about privacy issues surrounding the use of social media. Additionally, we will use the locator form to obtain limited contact information from individuals from the community who screen eligible and are interested in participating in the study. We will only obtain their phone number, an alternate phone number, and social media information to ensure we can reschedule individuals who do not show up for their first appointment. The locator form will be completed in REDCap. We will attempt to reach an individual once a week for four weeks; if we cannot reach them after four attempts, we will delete the record in REDCap.

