After the in-jail sessions, staff will meet with the participant within 10 days of release, check in by phone 1 month and 2 months after release, and meet with them in person again 3 months and 6 months after release. To facilitate follow up, during the one-on-one appointment with study staff in the attorney-client room, participants are asked to complete a detailed locator form and will choose a tentative time and date for the first post-release appointment based on the expected release date. The locator form shown in the Locator Form Appendix (attached to Research Protocol) is identical to the existing locator form approved under IRB protocol (#43520). The form is a strong retention tool tailored to this population. This form collects personal contact information (phone, email, address, etc), queries contact information for the participant and multiple key network members, and seeks consent to contact network members as needed. Our locator form asks participants to indicate whether they give permission for us to contact them via private messenger on social media (i.e., Facebook messenger) and language informing participants about privacy issues surrounding the use of social media. Research staff will monitor jail logs, JailTracker database, Courtnet, and Vinelink to identify when a participant gets released (as we know release dates can vary and change unexpectedly). Staff will contact the participant within the days following their release to schedule the first post-release appointment. At that appointment, staff will update the locator information as it is often the case that addresses, phone numbers, and other details may have changed. In addition to these strategies, staff will offer an appointment business card with the post-release appointment time, date, and location, and staff contact details with the person at the close of the one-on-one jail session. Because the person may be hesitant to take the card or lose the card, staff will also provide the card in a tamper-evident, tape-sealed envelope to jail staff so that they can place it with the individual's personal effects that they receive upon release. The envelope will also contain a printed local resource guide.

**Condition 6.** Information about the study is presented in a language understandable to prisoners.

**Describe what efforts have been made to present information about the study in a language understandable to the prisoner population:**

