All post-release sessions including completion of surveys may be held via phone due to policies related to the COVID-19 pandemic. Phone calls may be conducted through Facebook Messenger if the participant provided permission to be contacted by Facebook Messenger on the locator form. We will message individuals to set-up their follow-up appointment and in the message, ask their permission to conduct the follow-up interview via Messenger. We will only conduct phone (or video) interviews via Messenger if permission is provided and we will update their locator form. The locator form is routinely updated either in-person or by phone. The REHN may conduct these phone sessions remotely in the privacy of their home or in their office depending on current COVID-19 policies at the time of the session. If the session is conducted remotely, the REHN will conduct all activities in a private space, using their UK cell phone, laptop, and earbugs (or some other type of headset) and the study participant will also be in a private setting of their choice. The REHN will ask the study participants to answer a short security assessment at the time he/she schedules the session to ensure the individual is a study participant (see attachment in data collection section). If the individual does not answer all questions correctly, the REHN will not continue. If the individual answers all questions correctly, additional questions will be asked. These same questions will be repeated at the time of the phone session, confirming the identity of the study participant based on the initial responses provided.

Follow-up sessions including completion of surveys may take place in the jail via Zoom. We will host the interview using UK Zoom, which is HIPAA compliant. We will work closely with jail staff responsible for coordinating Zoom sessions to schedule the interview and to ensure the following:

- A confidential space will be available.
- A unique Zoom meeting ID will be provided to jail staff when the interview is scheduled.
- The waiting room feature will be enabled prior before the participant joins the session.
- The participant will join with video so study staff can confirm the individual's identity; once confirmed, the video will be disabled.

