**Post-release Intervention and Data Collection:** Participants will be compensated \$25 for completion of 3-month and \$25 for completion of 6-month follow-up surveys. Participants who update or verify their locator information between the baseline and 3-month and between the 3-month and 6-month follow-up will receive \$10 each time (total of \$20). Additionally, participants who refer individuals to the study and who screen eligible, will be offered \$10 for each referral, up to 3 individuals (total of \$30). This incentive structure and amounts are consistent with the IRB-approved CARE2HOPE UG3 (Protocol #43520). These amounts are commensurate with other studies, and not coercive. Payments will be made in cash for surveys completed in-person. Payments will be made by mailed cash card (e.g., electronic Visa card) for surveys completed by phone. Payments for follow-up surveys completed in jail (i.e., if a person is re-incarcerated) will be made on their commissary account, in-jail phone account, or provided in form of cash or gift card with personal belongings upon release (depending on policy of jail, as described above).

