### Exploratory Quantitative Analysis of START-C2H survey data:

Our community randomized trial consists of clustered data with participants nested within counties. To account for this "doubly-repeated" measures design, we will analyze all results using generalized linear mixed models. The covariance matrix for all observations within a county may be written as the Kronecker product of the compound symmetric covariance matrix for participants nested within county and a 2 by 2 residual covariance matrix for repeated measures nested within participants. Implementing the covariance model can be done in both PROC MIXED (for continuous measures) and PROC GLIMMIX (for categorical measures) in SAS by specifying a random intercept for county, and a compound symmetric residual matrix across time (repeated measures within participant). To estimate change in our primary outcomes due to the intervention we will begin by analyzing models of the following form:  $g(y) = \beta_0 + \beta_1 Time + \beta_2 Int + \beta_3 Time * Int$  where  $g()$  represents the appropriate link function for outcome  $y$ ,  $Time$  is a pre-post indicator variable, and  $Int$  is an indicator for the intervention group. The parameter of primary interest is  $\beta_3$ , the difference in slope between the intervention and control group. While our primary outcomes can be approximated as normally distributed, the link function  $g()$  will be modified as necessary to properly model the distribution for each outcome.

**Missing Data.** We will use multiple imputation to account for non-response over time and potential attrition. Additional augmentation variables found to be predictive of missingness will also be included in the imputation model. Ten imputations will be implemented. Additionally, we will use multiple imputation by chained equations to allow for imputation of non-normally distributed variables. All imputation analyses will be done using PROC MI and PROC MIANALYZE in SAS.

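### The plan has no rule for re-incarcerated time in the follow-up recall window, and items repeated from a 6-month or lifetime window do not cover equal exposure before and after

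*Combined protocol and SAP*

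**What the plan says.** Data Collection & Research Materials (survey content) states that "time periods at baseline refer to time before incarceration and, when repeated for follow-up visits, recall periods will be adjusted accordingly". The parenthesis that explains the adjustment says that "language referring to lifetime or past 6 month behavior will be changed to past 3 months". It mentions window length only and no restriction to time at liberty. The survey administration paragraph says that parts of the baseline survey are repeated at follow-up to measure change, and adds: "We will use timeline follow-back methodology to improve participant recall".

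Re-incarceration during follow-up is provided for. The COVID-19 Policies under Research Procedures say: "Follow-up sessions including completion of surveys may take place in the jail via Zoom". The Payment section says: "Payments for follow-up surveys completed in jail (i.e., if a person is re-incarcerated) will be made on their commissary account". On biological checks, the data collection section says: "We will not conduct drug screening in the jail".

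Jail records are followed for one stated purpose (Prisoners, Section 2, Condition 5): "Research staff will monitor jail logs, JailTracker database, Courtnet, and Vinelink to identify when a participant gets released".

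In the SAP's exploratory quantitative analysis, the model contains an intercept, Time, Int and their product. Time "is a pre-post indicator variable", and the target is the interaction, β3. There is no offset, custody covariate or rule for time in jail. Multiple imputation is planned for non-response and attrition.

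**The concern.** The team saw that custody distorts recall of drug use and moved the baseline window to before incarceration. No matching step is described at follow-up. A participant held in jail for part of the past 3 months has fewer days on which to use or inject. If the item is analysed as it stands, those days look the same as days at liberty without use.

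The trial's question is use among people living in the community. A navigation and treatment-linkage programme could plausibly change how often its participants return to jail. If it keeps them out, they have more days at risk and the programme looks weaker, or even harmful. If it leads to more jailing, it looks better.

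The second issue does not depend on re-incarceration. Under the stated rule, an item asked over 6 months or a lifetime at baseline is asked over 3 months afterwards, so the pre-post contrast subtracts quantities measured over different lengths of exposure.

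**Working it through.** **Inputs.** From the SAP power paragraph: 12 counties, 20 participants each (240 in all), within-county ICC 0.05, within-person correlation 0.35, alpha 0.10, power 0.80 at a standardized difference of 0.55. From the data collection section: a 3-month follow-up window. Assumed, because the documents give no figure: the jail share of the window (f), no use in custody, and the baseline mean in SD units (μ).

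**1. The plan's own power figure.**
- SD of change = √(2 × (1 − 0.35)) = 1.140.
- Design effect = 1 + 19 × 0.05 = 1.95, so the effective number per arm = 240 / 1.95 / 2 = 61.5.
- SE = 1.140 × √(2 / 61.5) = 0.206.
- With a two-sided 0.10 test on a noncentral t with 12 − 2 = 10 df, power at 0.55 is 0.801 and the minimum detectable effect is 0.5495.

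The plan states neither sidedness nor degrees of freedom, but this reading reproduces 0.80. The power statement is not in error.

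**2. Equal jail time in both arms.** With an identity link, the effect becomes 0.55 × (1 − f). The SD is held fixed.

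| Jail share f, both arms | Effect seen (SD) | Power |
|---|---|---|
| 0 | 0.55 | 0.80 |
| 10% | 0.495 | 0.72 |
| 20% | 0.44 | 0.64 |

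Under the null no false effect arises: rejection stays at 10%.

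**3. Unequal jail time.** Suppose use at liberty is unchanged in both arms. The mean change in an arm is then μ(1 − f) − μ = −fμ, and the spurious β3 = −(f_int − f_ctl) × μ.

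| Difference in jail share | μ (SD) | Spurious effect (SD) | Chance of rejecting a true null (nominal 10%) |
|---|---|---|---|
| 10 points | 1 to 2 | 0.10 to 0.20 | 13.5% to 23.6% |
| 20 points | 1 to 2 | 0.20 to 0.40 | 23.6% to 56.7% |

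The sign follows whichever arm is jailed more. An example in days, assuming use on 40% of community days in a 90-day window:
- Comparison jailed 20% of days: 90 × 0.40 × 0.80 = 28.8 use days.
- Intervention jailed 10% of days, no true effect: 90 × 0.40 × 0.90 = 32.4, an apparent harm of 3.6 days (+12.5%).
- Intervention with a true 25% reduction at liberty: 90 × 0.30 × 0.90 = 24.3, which against 28.8 appears as a 15.6% reduction.

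**4. Unequal windows.** Give a 3-month count variance 1, and let r be the correlation between the two 3-month halves of the 6-month baseline. The 6-month count has variance 2 + 2r. With pre-post correlation 0.35, the variance of change is 1 + (2 + 2r) − 2 × 0.35 × √(2 + 2r). With matched 3-month windows it is 2 − 2 × 0.35 = 1.3.

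| r | Variance of change | Ratio to 1.3 |
|---|---|---|
| 0 | 1 + 2 − 0.99 = 2.01 | 1.5 |
| 0.35 | 1 + 2.7 − 1.15 = 2.55 | 2.0 |
| 1 | 1 + 4 − 1.4 = 3.6 | 2.8 |

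Baseline imbalance is also over-corrected. Suppose the arms differ by δ per 3 months before and after, with no intervention effect. The pre difference is 2δ, the post difference is δ, and β3 is δ − 2δ = −δ instead of 0. With only 12 counties, some imbalance is to be expected.

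**The case against.** Several stronger readings are tempting, and the documents do not support them.

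- **That the plan counts jail days as time at risk.** No sentence says so. The 3- and 6-month surveys and the timeline follow-back form are attachments not reproduced here, and they may ask about days in jail. What stands is that no analysis in the SAP would use such information.
- **That custody necessarily produces a false effect.** It does so only if jail time differs by arm. No rate is given, overall or by arm, and the in-jail provisions describe contingencies.
- **That overdose is a main casualty.** The protocol says overdose is not a primary outcome, although the SAP's triangulation paragraph gives an overdose test as an example.
- **That drug screens would record jail-enforced abstinence.** Screens are not taken in jail. The concern is limited to self-report.
- **That every participant has an at-liberty baseline.** The anchor fits jail recruits. For community recruits, the pre-involvement window appears in the eligibility criteria, not in the survey text.
- **That variance rises 2.8-fold.** That is the upper end and needs perfectly correlated halves.
- **That use per community day should replace the planned outcome.** Use over calendar time, custody included, is a legitimate estimand. The per-day rate conditions on something that happens after assignment and drops anyone jailed throughout.

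Three further limits hold. The text available does not define the primary outcomes or say that a lifetime item serves as a pre value. Under a log link, a common ratio of window lengths is absorbed by the Time term and leaves β3 unchanged. The analysis is labelled exploratory.

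**Conclusion.** The concern holds in limited form. Followed as written, the plan lets custody during follow-up dilute self-reported use and injection effects, and it biases β3 if jail time differs by arm. The dilution is 0.55 SD to 0.495 or 0.44, with power about 0.72 or 0.64, for assumed jail shares of 10% or 20% and no use in custody. These results illustrate sensitivity and are not estimates for this trial. A uniform jail share would also shrink the follow-up SD somewhat, while jail time concentrated in a few participants could raise it.

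The unequal windows follow from the survey rule itself. For any 6-month count used as an outcome with an identity link, the variance of change is roughly 1.5 to 2.8 times that of matched windows. The SAP expects its primary outcomes to be approximately normal, so an identity link is the likely case.

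The point matters because the SAP's triangulation rule draws conclusions of no effect or of harm when quantitative and qualitative results agree. It merits a change to the plan, but it does not show that the result will be wrong.

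**What to change.** 1. **Equal exposure.** In the survey content text and the SAP model section, convert 6-month counts to per-day rates, or ask the same 3-month window at baseline. Do not use lifetime items as the pre value.
2. **Custody days.** Record days in custody within each follow-up window, from timeline follow-back checked against jail logs, and report them by arm. Log monitoring is described only for finding releases, so it must be extended through follow-up and to community recruits.
3. **Supportive analysis.** Keep the past-3-months outcome. Prespecify a supportive analysis of use per community day, with log community days as an offset or use as a proportion of community days. State that it conditions on a post-assignment quantity and omits participants with no community days.

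The cost is SAP wording, some extra record abstraction and one supportive analysis. If baseline interviews are complete, the per-day conversion is the usable form of item 1.

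### Recall windows shrink from lifetime or 6 months at baseline to 3 months at follow-up, and the pre-post model has no rule to make them comparable

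*Combined protocol and SAP*

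**What the plan says.** Under Data Collection & Research Materials, the survey administration paragraph says: "Sections of the baseline survey will be repeated at START-C2H's in-person session", including at 3 and 6 months, "to assess change over time". The survey content paragraph adds that "time periods at baseline refer to time before incarceration" and that, for follow-up, "language referring to lifetime or past 6 month behavior will be changed to past 3 months". No past-3-month baseline version of these items is described.

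The statistical section on START-C2H survey data fits an intercept, Time, Int and Time*Int, where Time "is a pre-post indicator variable". The parameter of primary interest is beta3, "the difference in slope between the intervention and control group". The residual is "a compound symmetric residual matrix across time (repeated measures within participant"), so pre and post share one variance. On scale, the section says: "While our primary outcomes can be approximated as normally distributed", the link function will be adapted to each outcome where needed. It does not mention window length, exposure time or conversion to rates.

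**The concern.** A question about the past 6 months and one about the past 3 months measure different quantities even if behaviour is constant. Counts halve, the proportion reporting any event falls, and a lifetime item can only be compared with something much narrower. A model that treats the two as one outcome measured twice reads part of the wording change as change over time.

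Three things are at stake:
- **The within-arm change, beta1.** It would look like improvement in both arms.
- **The precision of beta3.** A 6-month total varies more than a 3-month total, which adds noise to the change contrast.
- **The robustness of beta3 to baseline imbalance.** With 12 randomised counties and a mix of jail and community recruits, some imbalance is plausible.

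The hypothesis-test results then enter the joint displays used to conclude benefit, harm or no effect.

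**Working it through.** **Inputs.** From the Power paragraph: alpha 0.10, 12 counties, 20 participants per county, ICC 0.05, within-person correlation 0.35, power 0.80 at a standardised difference of 0.55. Assumed, because the documents do not say: a two-sided test, 120 per arm (240/2), and the ratio s of 6-month to 3-month SD.

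**The plan's own figure.** With equal windows and SD 1, Var(change) = 2(1 − 0.35) = 1.30. The design effect is 1 + 19 × 0.05 = 1.95. SE(beta3) = sqrt(2 × 1.30 × 1.95/120) = 0.206, so the noncentrality is 0.55/0.206 = 2.68. A noncentral t with 12 − 2 = 10 df gives power 0.801, matching 0.80. The match is not unique: some variants with 60 per arm also come out near 0.80.

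**Effect on beta1, with constant behaviour.**
- Counts: 4 events per month gives 24 at a 6-month baseline and 12 at a 3-month follow-up, in both arms.
- Any event, if successive 3-month windows are independent: P6 = 1 − (1 − P3)².

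| True 3-month prevalence | Reads at 6-month baseline | Apparent fall (points) |
|---|---|---|
| 20% | 36% | 16 |
| 40% | 64% | 24 |
| 60% | 84% | 24 |
| 80% | 96% | 16 |

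**Effect on the SE of beta3 (identity scale, no rescaling).** If every pair of 3-month windows correlates at 0.35, the 6-month total has variance 2 + 2 × 0.35 = 2.70 and covariance 0.70 with follow-up. Then Var(change) = 2.70 + 1 − 2 × 0.70 = 2.30, and the SE ratio is sqrt(2.30/1.30) = 1.33. If instead the baseline-to-follow-up correlation is fixed at 0.35, Var(change) = s² + 1 − 0.70s.

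| Assumption | Var(change) | SE ratio | Power at 0.55 follow-up SD |
|---|---|---|---|
| Equal windows | 1.30 | 1.00 | 0.80 |
| s = 1.41, correlation 0.35 | 2.01 | 1.24 | 0.64 |
| 0.35 throughout | 2.30 | 1.33 | 0.59 |
| s = 2, correlation 0.35 | 3.60 | 1.66 | 0.44 |

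Power uses the same noncentral t; for 0.35 throughout, SE = sqrt(2 × 2.30 × 1.95/120) = 0.273. The last row requires perfectly stable behaviour before baseline but only 0.35 correlation afterwards, so it is an extreme.

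**Effect of baseline imbalance on beta3, with no treatment effect.**
- Raw counts, identity link: 4.4 vs 3.6 events per month gives (13.2 − 26.4) − (10.8 − 21.6) = −2.4, half the baseline difference of 4.8.
- General form, if the standardised difference persists: the share absorbed is 1 − 1/s, which is 29% at s = 1.41 and 50% at s = 2. A one-SE imbalance is sqrt(2/120 × 0.95) = 0.126 SD if county effects cancel, or sqrt(2/120 × 1.95) = 0.180 SD if they do not. The shift is therefore 0.04 to 0.09 baseline SD. In follow-up SDs it is (s − 1) times the imbalance: 0.05 to 0.18.
- Counts, log link: log(0.5) − log(0.5) = 0.
- Any event, logit link: 3-month prevalences of 60% vs 50% give −0.15, and 65% vs 45% give −0.31. Rates of 0.05 and 0.08 per month (25.9% to 13.9%, and 38.1% to 21.3%) give −0.049, an odds ratio of 0.95.

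**The case against.** The strongest reply is that no affected outcome is shown. The primary outcomes are not named in the text, the survey instruments are attachments not reproduced, and only sections of the baseline survey are repeated. Drug screens and items on a short fixed window are untouched. This stands: the reach of the problem is unknown.

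Second, both arms receive identical surveys, so the common artefact falls in beta1 and cancels from beta3 when arms are balanced. This also stands. A reader might infer that the intervention effect is biased as a matter of course; the documents do not support that. Chance imbalance under randomisation is variance, and over repeated randomisations its effect is already part of the larger SE, so the two should not be counted as separate harms.

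Third, the plan allows the link to be modified. A log link for counts removes the distortion of beta3. A reader might cite the 0.05 and 0.08 rates as a spurious −4.8 points, but that is a risk difference, which the plan does not specify for categorical outcomes, and it starts from a 12.2-point baseline gap. A change of link does not rescue lifetime items, nor outcomes left on the identity scale.

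Fourth, a 3-month follow-up window is sensible in itself: it fits the 3-month visit and avoids overlap with the period before enrolment. What is missing is the matching baseline.

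Finally, the single residual variance is wrong when windows differ. With two complete time points, though, the pooled variance still reproduces the variance of the change: 2[(2.70 + 1)/2 − 0.70] = 2.30. The precision loss comes from the data rather than from the covariance structure.

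**Conclusion.** The concern holds in limited form, with moderate confidence. For any Time*Int outcome built on lifetime or past-6-month items, the stated wording rule and model give non-comparable pre and post values: beta1 is an artefact and, on the identity scale, beta3 is noisier and exposed to baseline imbalance.

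The most coherent estimate of the precision loss is an SE about 33% larger, taking 0.35 throughout; 24% to 66% covers the other assumed SD ratios, with the top end unlikely. The imbalance shift is modest beside the 0.55 detectable effect, and the half-share figure applies only to stable differences in behaviour rate. Lifetime items are the clearest problem. Most eligibility routes require recent opioid use or injection, so a lifetime item on either would be near ceiling at baseline and carry almost no information about change.

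The documents do not support a claim that the primary result is invalid or that every outcome is affected.

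**What to change.** In the SAP, list the recall window at baseline and follow-up for each outcome in the Time*Int model, and require the two to be equal. Where it can still be asked, or derived from the timeline follow-back already planned, use a past-3-month baseline covering the period before incarceration or enrolment.

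For data already collected:
- model counts as monthly rates, or use a log link with a log-time offset;
- allow unequal pre and post residual variances if windows still differ;
- keep lifetime items and unmatched any-in-period items out of the pre-post model.

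If the primary items already have matching windows, one sentence saying so settles the point.

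The cost is a short SAP rule and some recoding, plus a few reworded baseline items if enrolment is still open. The downside is that some 6-month and lifetime items drop out as change outcomes.
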